Environmental conditions (ambient OR temperatures, overhead lighting, electrical equipment), personal factors (personal protective equipment, metabolic heat, core and skin temperatures) and situational factors (type and length of a surgical procedure, perceived ergonomic workload) contribute to the presence of occupational heat stress experienced by surgeons performing surgical procedures. Surgeons' physiological and psychological responses to heat stress are measureable through a self-reported response to thermal comfort and perceived ergonomic workload, skin and core body temperature sensors, and a cognitive battery assessment. The physiological and psychological measure of surgeons' responses to heat stress can be influenced by wearing a cooling vest during the surgical procedure (Figure 1).

[figure not shown]

Figure 1. Conceptual Framework.

Methods

The trial will be conducted with Cleveland Clinic IRB approval and consent from participating surgeons. The trial will be registered at ClinicalTrials.gov. A full statistical analysis plan will be developed before any data are evaluated. Reporting will be consistent with the CONSORT guidelines.

Subject selection

Inclusion criteria are: 1) surgeons who perform elective major orthopedic surgery such as total hip and knee arthroplasties scheduled for 90 to 150 minutes at the Cleveland Clinic Main Campus; 2) Orthopedic surgeons ages of 25-65 years old, as body temperatures may be lower and less stable

in the elderly (Waalen & Buxbaum, 2011), who operate frequently enough to participate in four cross-over cases; 3) Surgical procedures in which surgical helmet systems or airborne barrier protection devices are worn are included as long as the surgeon wears the system for all four cases being measured.

Exclusion criteria are: 1) Surgical cases that require surgeons to sit on stools during the procedure, which may impact temperature and energy expenditure; 2) Surgeons who report having a recent illness within 24 hours prior to the surgery, symptoms producing a febrile condition; 3) Surgeons who worked the previous evening; and 4) Surgeons who wear lead X-ray gowns.

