Surgeon research subjects will be recruited by posting information about the study on the Orthopedic and Rheumatology Institute website. All human subject research protocols instituted by the Cleveland Clinic will be followed and documented. Participating surgeons will be advised of all known risks and benefits of study as well as information describing the requirements of the study and data management. The surgeons will be advised of the option to stop participation at any time. Written informed consent will be obtained from each surgeon.

Participating surgeons will be assigned a study number and only this number will be included on case-report forms. A single cross-linking record will identify specific surgeons for the purpose of organizing cross-over cases. Otherwise, analysis will be based on study number and no individual data will be linked to specific surgeons. Case-report forms will be kept locked in a secure research office and data-acquisition iPads will be encrypted.

We do not plan to obtain consent from patients for this comparative effectiveness trial that evaluates an FDA exempt device designed to improve *surgeons' comfort*.

Protocol

We propose a randomized cross-over trial using a uniform and strongly balanced 4-period design in which will include four operations for each surgeon. Surgeons will be randomized to 1 of 4 sequences: ABBA, BAAB, AABB or BBAA. The design is “uniform” in that each treatment appears the same number of times within each sequence (uniform within sequence) and if each treatment appears the same number of times within each period (uniform within each period). It is strongly balanced with respect to first-order carryover effects because each treatment precedes every other treatment, *including itself*, the same number of times.

We chose this design versus a parallel group design because 1) it removed the potential for confounding, even with a small sample size, as comparisons are made within subject, and not between subjects; 2) the design is very efficient since within-subject comparisons are correlated, obviating the need for a larger study which would also not be practical in this setting. Also, no differential carryover effect is expected in this study, removing one of the main concerns with crossover trials.

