Surgeons will be randomly assigned to use either the CoolSource™ cooling vest (worn between scrubs) and a conventional surgical gown for each of 4 surgeries. Sequence of treatments within surgeons will be randomized (ABBA, BAAB, AABB or BBAA), and determined using the PLAN procedure in SAS, such that each surgeon will wear vest and non-vest twice. The sequencing will not be shared with any study personnel. Allocation for each case will be concealed with a web-based system that will be accessed only shortly before surgery.

We will target an ambient temperature of $21^{\circ}\text{C} \pm 1^{\circ}\text{C}$, and try to maintain the same temperature of each of the four study cases for each surgeon. The CoolSource vest holds six reusable cooling packs

located bilaterally on the shoulders, angled flank along the base of the rib cage, and along each side of the spine, mid-back. The vest will be donned over hospital-issued scrubs after all temperature sensing devices have been applied and before surgical hand scrubbing. Surgeons will wear the vest throughout surgery, and for a few additional minutes while postoperative assessments are made (details below).

The weight of the disposable cooling vest is 1 kg which is evenly distributed over both shoulders. The cooling packs have an insulated cover to reduce condensation or sweating while seated inside the vest pocket. The flexible frozen reusable cooling packs will be inserted into each of the six pockets and the vest belt will be tied to hold the cooling packs securely. The disposable cooling vests will be discarded after each case, and the cooling packs returned to a freezer.

Measurements

A questionnaire detailing demographic information (age, height, weight, age, ethnicity, and education level) training level, specialty program, and estimated past case volume will be completed by participating surgeons before their first case.

Temperature of the freezer holding the cooling packs will be assessed before randomization to confirm that the temperature is <0°C.

Before every surgical case starts the time the surgeon dons the cooling vest and the time the surgeon dons the sterile surgical gown will be recorded.

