The research study is being conducted according to the purposes outlined in the research protocol and the primary responsibility of the informed consent is designed to protect the rights, welfare, and well-being of the participants. The risks and benefits of the study are reasonable to the anticipated benefits and the importance of generalizable knowledge that is expected to result.

Identified Risks:

- Risks to breach of confidentiality: The records of this research will be kept confidential and every effort will be made to protect participants' confidentiality through encrypted coded data and will not include any information that will make it possible to identify a participant. Any reports that may be published will not include any information that will make it possible to identify a participant. Research records will be kept in a locked file and access will be limited to the researchers and hospital review board responsible for protecting human participants.
- Participants will be advised of the entire protocol as well as the voluntary option to withdraw from the study at any time.
- Shaving small skin areas (approximately 2" x 2") for temperature sensor placement may be necessary for adhesive cover to adequately adhere to skin surfaces which could cause mild discomfort, redness, or itching as the body hair regrows.

- Potential risks to comfort, elevated body temperatures, and cognitive performance (e. g. short-term memory and/or processing speed) in occupational heat stress studies naturally occur while surgeons are operating, however, the cooling vest intervention administered in the study may reduce these potential risks.
- There is no evidence that OR personnel wearing the cooling vest under the impervious sterile surgical gown offer any risk to patients as there is no direct contact.

Steps to minimize risks:

- Attenuate first-time cooling-vest users' concerns for perception of discomfort related to cooling packs or added weight, all participants will have the opportunity to wear the cooling-vest prior to any of the randomized trials.
- All members of the research team will be appropriately trained, maintained appropriate credentials, licensing privileges, and institutional competencies.

Identifying benefits:

- The vest design was designed to cool areas of the body that do not cause discomfort over a period of approximately two hours, and the cooling packs do not come in direct contact with participant's skin as it is worn over scrubs.

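### Allocation is said to be concealed for every case, but the first two assignments determine the last two, and no rule states how a surgeon's study cases are selected

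*Combined protocol and SAP*

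**What the plan says.** The Protocol section of Methods describes a "4-period design in which will include four operations for each surgeon" and lists the permitted orders: "Surgeons will be randomized to 1 of 4 sequences: ABBA, BAAB, AABB or BBAA". Each surgeon's sequence is generated in SAS, "such that each surgeon will wear vest and non-vest twice". Two safeguards follow. One concerns staff: "The sequencing will not be shared with any study personnel". The other concerns each operation: "Allocation for each case will be concealed with a web-based system that will be accessed only shortly before surgery".

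The trial is open to the surgeon, who experiences the assignment directly: "Surgeons will wear the vest throughout surgery, and for a few additional minutes while postoperative assessments are made". Under Identified Risks the plan adds: "Participants will be advised of the entire protocol as well as the voluntary option to withdraw from the study at any time".

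Subject selection admits "elective major orthopedic surgery such as total hip and knee arthroplasties scheduled for 90 to 150 minutes". It excludes cases done seated and surgeons in lead gowns, and requires helmet use to be the same across a surgeon's four cases. Nothing states when or by whom the four study operations are picked from a surgeon's eligible list.

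**The concern.** Concealment matters because it stops knowledge of the coming treatment from influencing what is enrolled under it. Here the surgeon is randomized, but each period is filled by an operation, and operations differ. If the allocation of cases 3 and 4 can be worked out in advance, a late-opening web system protects nothing for those cases.

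The conceptual-framework paragraph just before Methods itself names the type and length of a procedure as contributors to heat stress. A surgeon or scheduler who knew that the next study case was a vest case could place a longer or harder operation there, or the reverse. The within-surgeon comparison does not cancel this, because the surgeon is the same and the operation is not. The Protocol section's argument that within-subject comparison removes confounding therefore does not extend to case selection. Steering of this kind could affect measured temperature, exertion and fatigue as well as the thermal comfort rating.

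**Working it through.** **Inputs.** From Protocol: four sequences (ABBA, BAAB, AABB, BBAA), four cases per surgeon, two of each treatment. From Sample Size Justification: 26 surgeons, a 2-point difference, SD 3, within-subject correlation 0.5, power 90%, alpha 0.05 (taken as two-sided; sidedness is not stated). From Data Analysis: models with treatment, sequence and period, and subject as a random effect. Assumed, not in the documents: b and f, defined in step 4.

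**1. The plan's own figure.** The SD of the difference is √(2×9 − 2×0.5×9) = 3. A two-sided paired t-test at 0.05 for a difference of 2 needs n = 26 (power 0.904). The stated sample size is reproduced and is not in dispute.

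**2. What the first two cases reveal.**

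| First two cases | Possible continuation |
|---|---|
| AB | BA only |
| BA | AB only |
| AA | BB only |
| BB | AA only |

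Share of allocations determined by earlier ones: case 1, 0%; case 2, 0%; case 3, 100%; case 4, 100%. That is 2 of 4 per surgeon, or 26 × 2 = 52 of 26 × 4 = 104.

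A person who knows only that each treatment is used twice, and not the list, can deduce case 4 always and case 3 for the two sequences that start AA or BB: (0 + 0 + 0.5 + 1)/4 = 37.5%.

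**3. Is the sequence set as described?** Yes. Each period has each treatment in two of the four sequences, and AA, AB, BA and BB each occur three times as consecutive pairs. The design is uniform and strongly balanced as claimed.

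**4. Bias if case placement depends on allocation.** Let A be the vest (the result is the same with the labels reversed). Suppose placement shifts the rating by sA in vest cases and sB in non-vest cases, in periods 3 and 4 only. The shift in a surgeon's vest-minus-no-vest mean is:

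- ABBA: (sA − sB)/2
- BAAB: (sA − sB)/2
- AABB: −sB
- BBAA: sA

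The average is [(sA − sB) + (sA − sB)]/4 = (sA − sB)/2. Writing b = sA − sB, the bias is b/2 if all surgeons steer the same way, and f × b/2 if a fraction f do and the rest do not steer. A least-squares fit with surgeon, period and treatment terms for 26 surgeons split 7/7/6/6 also gives 0.5 for b = 1, so the planned adjustment does not remove it.

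**5. Range for f = 1** (paired t, n = 26, SD of difference 3):

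| b (assumed) | Bias b/2 | Share of 2 points | False-positive rate | Power at a true 2 points, bias against the vest |
|---|---|---|---|---|
| 0.25 | 0.125 | 6.25% | 5.5% | 86% |
| 0.5 | 0.25 | 12.5% | 7% | 82% |
| 1 | 0.5 | 25% | 13% | 69% |
| 2 | 1.0 | 50% | 37% | 37% |

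With f = 0.5 the bias halves, to 0.0625 to 0.5 point.

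**6. Would the planned interaction test catch it?** Such a shift is a treatment-by-period interaction, which the plan tests as a check for carryover. With SD 3 and correlation 0.5, that 3-degree-of-freedom test at 0.05 has about 10% power at b = 1 and 27% at b = 2, so it is not a safeguard.

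**The case against.** Much of this predictability comes with any open crossover that gives two of each treatment: case 4 is always deducible. Adding ABAB and BABA would lower the determined share only from 50% to 33%, and would lose the strong balance. Nothing suggests that concealment of the sequence at a surgeon's entry fails. This stands, and it is why the sequences should stay.

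A reader might infer that cases 3 and 4 are picked after their allocation is known. The documents do not say so. Operations may be chosen one at a time or booked together, and if all four were fixed in advance, foreknowledge could not affect which cases were used. What can be said is that no rule fixes them.

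A reader might also infer that the self-rated primary outcome is biased by the loss of concealment. That mixes two mechanisms. The surgeon knows the treatment when rating all four cases, whatever the concealment. Predictability adds only the possibility of selective placement.

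Finally, there is no evidence of motive or direction. Steering in opposite directions by different surgeons cancels. The 90 to 150 minute window, the seated-case and lead-gown exclusions, consistent helmet use and the ambient temperature target narrow the room to steer. They leave difficulty, and duration within the window, open.

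**Conclusion.** The concealment statement is wrong for cases 3 and 4. This is exact: the first two assignments identify the sequence, so 52 of 104 allocations are deducible by anyone who knows the list and those assignments. That includes surgeons, who are told the protocol, and could include staff present at the first two cases. Because case selection is unspecified and the models adjust for no case characteristic, selective placement in periods 3 and 4 is possible and would pass through the analysis.

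The size of any bias is not known. It is f × b/2, or 0.125 to 1.0 point for f = 1 and b from 0.25 to 2. Both quantities are assumptions, and a net effect requires steering in a common direction. The result is a risk to be closed and not evidence that bias will occur. It does not make the crossover design invalid and does not affect the sample size. The point should be addressed, since the plan claims a property that its design lacks and the remedy cannot be applied once the cases are done.

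**What to change.** Keep the four sequences, the sample size and the models. Add a case-selection rule in one of two forms:

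- before a surgeon's first allocation is revealed, list and lock that surgeon's four study cases in the web system; or
- pre-specify a non-discretionary rule, such as the next eligible scheduled case on successive operating days.

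Replace a cancelled or newly ineligible case by the same rule, and log the reason and its timing relative to the earlier allocations.

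Correct the concealment sentence in Protocol to say that allocation is unpredictable only for cases 1 and 2, that cases 3 and 4 are deducible, and that protection against selective placement there rests on the lock or rule. The lock limits the consequence of predictability; it does not restore concealment, and the text should not suggest that it does.

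The cost is a short procedural amendment, a log and less scheduling flexibility. Some risk remains. The exclusions for recent illness and for work the previous evening can arise close to surgery, so a locked case 3 or 4 may have to be replaced when its allocation can already be deduced. A scheduler who knows the allocation could also still arrange the list under a next-eligible rule. The log makes replacements visible.

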Decrements in **cognitive performance** occur when core temperature increases by about 1°C (Reinersten et al., 2008; Simmons et al., 2008). The level of cognitive decline depends on exposure duration, the intensity and complexity of the activity, and— importantly— the degree of hyperthermia (Gaoua et al., 2011; Simmons et al., 2008). There have been several heat stress studies performed in industrial settings and in climatic heat chambers. Processing speed and reaction time, short-term memory, and decision are all impaired (Gaoua et al., 2011; Sun et al., 2012; Piil et al., 2017; Mazlomi et al., 2017).

Cooling the skin reduces the unpleasant sensations caused by excessive heat exposure (Simmons et al., 2008). Localized cooling of the torso during systemic heat exposure reduces physiological stress by lowering body skin and core temperatures, decreasing heart rate, reducing sweat rate, and improving perception of thermal comfort (Chang, Song, & Yang, 2015). **Cooling vests** worn under impervious surgical gowns serve as a heat sink and reduce unpleasant sensations and the symptoms of physiological stress (Smolander et al., 2004; Kenney et al., 2011; Reinersten et al., 2008).

We propose to test the primary hypothesis that **wearing a cooling vest during surgery improves surgeons' perception of thermal comfort**. Secondary, we will test the hypothesis that **wearing a cooling vest during surgery reduces surgeons' mean-body temperature and preserves their cognitive performance**.

Specific Aims

1. Our **primary aim** is to evaluate surgeons' self-rated thermal comfort with and without a cooling vest during prolonged and strenuous surgery.
Primary hypothesis: Surgeons' self-rated thermal comfort is improved by wearing a cooling vest during prolonged and strenuous surgery.
2. A **secondary aim** is to evaluate surgeons' mean-body temperature with and without a cooling vest during prolonged and strenuous surgery.

Secondary hypothesis 1: Surgeons' mean-body temperature, estimated from core and mean-skin temperature, is reduced by wearing a cooling vest during prolonged and strenuous surgery.

3. Another **secondary aim** is to evaluate surgeons' cognitive performance with and without a cooling vest just after prolonged and strenuous surgery.

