Primary Outcome will be self-rated thermal comfort. Immediately after surgery, *while still gowned*, surgeons will rate their thermal comfort on a 0-10 Likert scale, with 0 representing extreme cold, 5 being thermal comfort, and 10 representing extreme heat. Two points on the 11-point Likert scale will be considered a clinically important difference.

Secondary Outcome #1 - mean core temperature. The first secondary outcome will be the mean core temperature for a case, calculated as the time-weighted average over the taken measurements. The surgeon's core body temperature will be monitored by a validated wireless wearable iThermonitor WT701 biosensor which estimates core temperature within $\pm 0.5^{\circ}\text{C}$ (Pei et al., 2018). The sensor will be applied to the surgeon's right axilla 15-20 minutes prior to the surgical hand scrub performed at the start of surgery and secured with an adhesive cover. A small patch of axillary hair will be clipped or shaved as necessary. After the temperature sensors are applied, the surgeon's oral temperature will be measured by the Femometer adult digital oral thermometer which meets professional accuracy standards for digital thermometers (ASTM E1112-00) to support the accuracy of the iThermonitor core body temperature measurement. The surgeon's oral temperature will be measured for a second time when the surgeon exits the surgical field prior to taking the C3B battery assessment.

Secondary Outcome #2 - mean skin temperature. The second secondary outcome will be the mean skin temperature for a case, calculated as the time-weighted average over the taken measurements. Mean skin temperature will be estimated from skin temperature from the back of the upper chest, deltoid arm, thigh, and calf using the formula $[\text{MST}_R = 0.3 t_{\text{chest}} + 0.3 t_{\text{arm}} + 0.2 t_{\text{thigh}} + 0.2 t_{\text{leg}}$ or $0.3(t_{\text{chest}} + t_{\text{arm}}) + 0.2(t_{\text{thigh}} + 0.2 t_{\text{leg}})]$ (Ramanathan, 1964). Skin temperature will be continuously measured using wireless patches, TempTraq, which meet professional accuracy standards for digital thermometers (ASTM E1112-00). The sensors will remain affixed with adhesive dressing on the surgeon's body surface throughout surgery and approximately 10 minutes required for post-operative testing.

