Participants' age, weight, height, and other continuous demographics and baseline characteristics will be summarized using descriptive statistics (n, mean, median, standard deviation, minimum and maximum), while race, surgical specialty, as well as other categorical variables will be summarized with frequency tabulations. The 4 sequence groups will be compared on baseline variables descriptively.

Specific Aim 1) Evaluate the difference between surgeons' self-rated thermal comfort with and without a cooling vest during prolonged and strenuous surgery. 0-10.

Perceived measure of thermal comfort for both conditions, with and without a cooling vest will be analyzed by descriptive statistics recommended for ordinal Likert scale items – i.e., frequencies and median [quartiles].

We will use a linear mixed effects model to test the treatment effect of the cooling vest on mean thermal comfort. We will adjust for treatment, sequence and period effects, and include subject as a random effect to account for the within-subject correlation. We will test for differential carryover effect by assessing the treatment-by-period interaction. If no interaction is detected the interaction term will be removed and the treatment effect assessed in a main effects model.

Specific Aim 2) Evaluate the difference between the surgeons' core, mean skin, and mean body temperatures with and without a cooling vest during a prolonged strenuous surgery.

For each temperature we will used a linear mixed effects model to test the treatment effect of the cooling vest on a subject's temperature during the case. We will adjust for treatment, sequence and period effects, and include subject as a random effect to account for the within-subject correlation. We will test for differential carryover effect by assessing the treatment-by-period interaction. If no interaction is detected the interaction term will be removed and the treatment effect assessed in a main effects model.

Specific Aim 3: Evaluate the difference between the surgeons' measure of cognitive performance with and without a cooling vest just after a prolonged strenuous surgery.

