Cognitive performance will be measured by the C3B performance-based battery of cognitive tests at the end of the case. An overall score for a subject after a particular case will be calculated by first rescaling (e.g., so that each item ranges from 0 to 100) and then averaging the scores across the battery. Treatment effect will be assessed using a linear mixed effects model as described for Aims 1 and 2.

The significance level will be 0.05 for the primary outcome (Aim 1) and 0.05 across the 3 secondary outcomes (2 temperatures, cognitive function), such that the secondary outcomes will be assessed at a significance criterion of $0.05/3=0.017$. SAS statistical software version 9.4, Carey, NC, will be used for all analyses.

Specific Aim 4: Evaluate the difference between the surgeons' perceived ergonomic workload with and without a cooling vest during a prolonged and strenuous surgery.

Perceived ergonomic workload will be measured by duration of the surgical procedure recorded in minutes, surgeons' report of the number of hours slept prior to the study day, Borgs' visual analog scale for exertion (0-10), and the Rating of fatigue scale (0-10).

Perceived ergonomic workload for both conditions, with and without a cooling vest will be analyzed by descriptive statistics recommended for ordinal measured items – i.e., frequencies and median [quartiles].

We will use a linear mixed effects model to test the treatment effect of the cooling vest on mean perceived levels of exertion and fatigue. We will adjust for treatment, sequence and period effects, and include subject as a random effect to account for the within-subject correlation. We will test for differential carryover effect by assessing the treatment-by-period interaction. If no interaction is detected the interaction term will be removed and the treatment effect assessed in a main effects model.

Sample Size Justification.

Sample size calculation is based on having 90% power at the 0.05 significance level to detect a difference of 2 or more (on a scale of 0-10) on surgeons' self-rated thermal comfort with and without a cooling vest. With an estimate SD (s) of 3 for thermal comfort in each group, and an assumed within-subject correlation (ρ) of 0.5, the estimated SD of the within-subject difference would be

$$\sqrt{s_1^2 + s_2^2 - 2\rho s_1 s_2}, \text{ or } \sqrt{2(3^2) - 2(0.5)(3)(3)} = 3.$$

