Within these assumptions we would need a total of 26 subjects to have 90% power to detect a difference of 2 or more on mean thermal comfort in this crossover design. The detectable difference corresponds to an effect size (Cohen's D) of 0.66, which is medium to large. For the 3 secondary outcomes each using a significance criterion of $0.05/3=0.017$, we would have 90% power to detect an effect size of 0.76.

Our assumptions of variability and within-subject correlation for the primary aim will be reassessed in an internal pilot study after 13 subjects have completed the 4 cases, and the total sample reassessed based on the findings.

To ensure that sensors, iPad, and wireless technology can be monitored during a real-time surgical procedure, a small trial of two or three case studies will be conducted to ensure all processes work properly, which will not be included in the final data analysis. Periods of poor data or lead disconnection will be marked for exclusion in analysis.

Innovation

The discomfort surgeons experience during long surgical procedures combined with an inability to evaporate sweat through impervious surgical gowns prompted the innovative design of the disposable CoolSource™ Cooling System. The cooling vest is worn by surgeons under the impervious gown to reduce heat and improve comfort while performing surgery. The positive changes in mood, attention, and productivity have been reported by staff and surgeons in a product trial which supported the need for research to investigate the impact heat stress has in which supported the need for research to investigate the impact heat stress has in *real-time* operating conditions.

The **innovative** design of this study measures data by wireless sensor technology during *real-time* surgical procedures without disrupting the surgery, as previous studies utilized simulated conditions. Furthermore, limitations are numerous when trying to generalize findings discovered in structured simulated studies as there is a wider range of effecting factors in *real-time* investigations (Mazlomi et al., 2017). Information obtained from this study will support the development of prescriptive measures and standards to address heat stress in surgeons to alleviate perceptions of discomfort and improve physiological and psychological well-being.

Protection of Human Subjects

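### The primary rating puts comfort at 5, but the test, the 2-point threshold and the sample size use the raw mean, so a significant result shows 'cooler', not necessarily 'more comfortable'

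*Combined protocol and SAP*

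**What the plan says.** Under Measurements, the primary outcome is one rating from 0 to 10, given straight after surgery, "with 0 representing extreme cold, 5 being thermal comfort, and 10 representing extreme heat". The best value is therefore in the middle of the scale. The same paragraph adds: "Two points on the 11-point Likert scale will be considered a clinically important difference". It gives no direction and does not refer to 5.

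The primary hypothesis in Specific Aims is about comfort: "Surgeons' self-rated thermal comfort is improved by wearing a cooling vest during prolonged and strenuous surgery".

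The Specific Aim 1 analysis is: "We will use a linear mixed effects model to test the treatment effect of the cooling vest on mean thermal comfort". No recoding of the rating is stated. Frequencies and medians with quartiles are also planned, as "descriptive statistics recommended for ordinal Likert scale items", but they are not tied to the conclusion.

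The Sample Size Justification works on the same raw scale. It starts "With an estimate SD (s) of 3 for thermal comfort in each group", assumes a within-subject correlation of 0.5, and arrives at 26 surgeons to "detect a difference of 2 or more on mean thermal comfort in this crossover design". A later check is planned: "Our assumptions of variability and within-subject correlation for the primary aim will be reassessed in an internal pilot study". It does not revisit how the rating is scored.

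**The concern.** On a scale with its optimum at 5, a fall of 2 points has no fixed meaning for comfort. From 8 to 6 the surgeon moves nearer comfort, from 6 to 4 stays equally far away, and from 5 to 3 moves further off. The planned model scores all three alike.

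What is at stake is the wording of the primary conclusion. A significantly lower mean with the vest could be reported as improved comfort without any check that ratings moved towards 5. Even where the direction is right, the gain in comfort can be smaller than the raw fall, so the 2-point threshold need not describe a 2-point gain in comfort.

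**Working it through.** **1. The plan's own figure.** SD of the difference = sqrt(2 x 3^2 - 2 x 0.5 x 3 x 3) = 3. A two-sided paired t-test at 0.05 for a difference of 2 has power 0.892 with 25 surgeons and 0.904 with 26. N = 26 reproduces, which confirms that the trial is sized on the raw difference.

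**2. Break-even for direction.** Let both conditions have the same symmetric shape, with means m0 (no vest) and m1 = m0 - d. Mean |rating-5| then depends only on how far the mean lies from 5, and does not decrease with that distance. It falls only if |m1 - 5| < |m0 - 5|, that is, if (m0 + m1)/2 > 5, or m0 > 5 + d/2. For d = 2 this is m0 > 6; for d = 1 it is m0 > 5.5.

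**3. Condition for equal size.** The raw change and the change in |rating-5| are equal in size if every rating in both conditions is 5 or higher, and nearly equal if almost all are.

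**4. Size under the actual design.** Assumptions not in the documents: the no-vest and vest means shown, and the shapes. From the documents: 26 surgeons, four sequences (split here 7, 7, 6, 6), two ratings per condition, SD 3, correlation 0.5. Ratings were rounded and cut to 0-10, and treatment and period effects were estimated within surgeon. Each case has 20,000 simulated trials.

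| No-vest to vest mean | Raw test significantly lower (SD 3, cut) | Change in mean distance from 5: SD 3, cut | SD exactly 3, fall exactly 2 | SD 2, cut |
|---|---|---|---|---|
| 8 to 6 | 99% | -0.68 | -1.31 | -1.19 |
| 7 to 5 | >99% | -0.37 | -0.69 | -0.70 |
| 6 to 4 | >99% | 0.00 | 0.00 | 0.00 |
| 5 to 3 | >99% | +0.37 | +0.69 | +0.70 |

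The fourth column uses maximum-entropy distributions on 0-10. In the SD 3 cut case the observed SD is 2.4 to 2.8 and the observed fall 1.66 to 1.80. Rejection exceeds the planned 90% because each surgeon gives two ratings per condition: the residual variance is 9 x 0.5 = 4.5, so before cutting the SD of a surgeon's mean difference is sqrt(4.5/2 + 4.5/2) = 2.12 rather than 3. With one rating per condition, the raw test rejects in about 87-89% of trials in all four cases.

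**5. The planning SD.** Ratings confined to 5-10 with mean m have SD at most sqrt((10 - m)(m - 5)), which peaks at 2.5 when m = 7.5. An SD of 3 is thus incompatible with all ratings at 5 or higher. Over all distributions on the integers 0-10 with SD 3, the smallest possible share below 5 is 5.5% (at mean 7.5), about 0.055 x 52 = 2.9, or 3 of 52 ratings per condition.

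**6. What a check on |rating-5| would do.** Share of trials with a significantly lower raw mean and, in addition, the result shown:

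| Means | Estimate below 0 (SD 3, cut) | Whole 95% interval below 0 (SD 3, cut) | Whole 95% interval below 0 (SD 2, cut) |
|---|---|---|---|
| 8 to 6 | 98% | 56% | 99% |
| 7 to 5 | 86% | 20% | 62% |
| 6 to 4 | 49% | 2.5% | 2.5% |
| 5 to 3 | 12% | 0.1% | 0.0% |

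The interval here comes from each surgeon's vest minus no-vest difference. At 6 to 4, the random-intercept model fitted to |rating-5| is falsely significant on the low side in 3.8-5.2% of trials, because taking distances makes the vest effect differ between surgeons. Surgeon-level differences give 2.5%.

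**The case against.** The strongest reply is that surgeons are hot, so lower is better. The Introduction describes them as soaked in sweat under impervious gowns, and the rating is taken at the end of surgery while still gowned. At a no-vest mean of 7 to 8, raw mean and distance from 5 move the same way. This stands, and the harmful cases need a no-vest mean of about 6 or lower, which runs against that premise. But the plan neither states a no-vest mean nor makes the premise a condition of its conclusion.

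The planned frequencies and quartiles would show cold-side ratings to an attentive reader. That also stands, but they do not govern what is concluded. The full analysis plan that Methods promises before data are evaluated could settle the scoring; the text supplied does not.

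Three stronger readings are tempting and not supported:

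- A reader might infer that a lower mean signals better comfort only if nearly all ratings are 5 or higher. That is needed for the sizes to match, not the direction. With SD exactly 3 and means 8 to 6, 15% of no-vest and 32% of vest ratings are below 5, yet mean distance falls by 1.31.
- A reader might take the SD of 3 as a forecast of cold-side ratings. It is an unsourced planning value, to be reassessed after 13 surgeons. It is inconsistent with all ratings at 5 or higher, but it is not evidence of where they will fall.
- A reader might see overcooling in Protection of Human Subjects. Its concern about cooling packs or added weight is for first-time users and does not mention feeling cold. Its no-discomfort statement covers about two hours, while cases are scheduled for up to 150 minutes; this limits the statement and does not show overcooling.

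**Conclusion.** The concern holds as a gap between the hypothesis and the test. That the plan tests and sizes a raw mean on a scale with its optimum at 5, with no rule for ratings below 5, is clear from the text, and confidence in this is high.

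The consequence depends on an unknown no-vest mean. At 7 to 8 the direction is right, but the gain in comfort can be well below the raw fall (0.37 to 1.31 points in the SD 3 cases, for a nominal 2-point fall). At 6 or below, the raw test would still be significant with no gain or a loss. These sizes rest on the assumed means, shapes and SDs above, and how likely each case is cannot be judged from the documents. The N = 26 arithmetic is correct for the raw difference. This should be fixed, because it decides what the primary result may be called and has to be settled before the data are seen.

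**What to change.** Keep the raw-score primary model and N. Before data are evaluated, add to Specific Aim 1:

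- *Improved* means closer to 5. A significantly lower raw mean by itself will be reported as cooler thermal sensation.
- Beside the primary result, report the vest effect on |rating-5| with a 95% confidence interval computed from each surgeon's vest minus no-vest difference, and the share of ratings below 5 by condition.
- Word any conclusion on comfort from that estimate and interval. If the estimate is zero or higher, conclude only that sensation was cooler. If it is below zero but the interval includes zero, say that movement towards comfort was not established.

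The sign of the estimate alone should not be the gate: it would claim improvement in about 49% of trials with no true change (6 to 4).

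The cost is a few sentences and no extra data or surgeons. The price is a more cautious claim. At SD 3 cut to 0-10, the interval excludes zero alongside a significant raw test in about 56% of trials at 8 to 6 and 20% at 7 to 5; at SD 2, in about 99% and 62%. Also, |rating-5| treats equal distances on the hot and cold sides as equally bad, which the documents do not state, so the sponsor should say whether it accepts this.
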